### Data analysis plan

Quantitative variables will be described by means and standard deviations whereas median with interquartile range will be mentioned for qualitative variables. Frequencies and percentages will be calculated for the knowledge, attitude, and practices of adolescents regarding nutrition and WASH. The comparison between intervention and control at baseline and end line will be performed by using paired t-test and Chi-square. For the variables that are not normally distributed, a nonparametric test McNamara will be used. Binary logistic regression and multiple linear regression will be used to assess the effect of intervention. All the statistical analyses will be conducted using SPSS version 23. A p-value less than 0.05 will be considered statistically significant.

Descriptive	Inferential

 
• Mean, SD Normally distributed
 
• Median, interquartile range Skewed distribution
 
• Percentages and frequencies of knowledge, attitude, and practices
 
	
 
• Chi-Square-McNamara knowledge, attitude, and practices
 
• T- test paired Continuous variables
 
• Binary logistic regression and multiple linear regression
 
• Proportion changes - chi-square Observational checklist
 

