### **Data collection tool/instrument**

Data will be collected through adopted and adapted self-administered, structured questionnaires from 6,7, and 8-grade school-going adolescents at baseline and the end line. The questionnaire will be categorized into four main groups to assess the respondent's demographic data and their knowledge, attitude, and practices (KAP) about nutrition and WASH. Group A (demographic characteristic), group B contains physical assessment, group C included 24 Questions on KAP on nutrition that are adopted from the KAP manual developed by the Food and Agriculture Organization of the United Nations (2014) and group D are based on the 16 WASH items adopted from GSHS version 2013. The questionnaire will be translated into the Urdu language. Observation of the eating practices, school canteen, WASH, and school environment will be assessed through a checklist at baseline and end line.

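### The only tests tied to the 40-item knowledge, attitude and practice questionnaire are chi-square and McNemar at p<0.05; a few pre-specified scores would answer the question better

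*Protocol*

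**What the plan says.** The instrument is described in the Protocol, Phase II, Data collection tool/instrument. On nutrition, "group C included 24 Questions on KAP on nutrition". On water, sanitation and hygiene, "group D are based on the 16 WASH items adopted from GSHS version 2013". That makes 24 + 16 = 40 items, asked at baseline and end line.

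The Data analysis plan of the same phase states: "Frequencies and percentages will be calculated for the knowledge, attitude, and practices of adolescents regarding nutrition and WASH". In its table the inferential entry for these items is "Chi-Square-McNamara knowledge, attitude, and practices" (the McNemar test is meant). The entry "T- test paired Continuous variables" is a separate line, as are the mean and standard deviation. The threshold is common to everything: "A p-value less than 0.05 will be considered statistically significant".

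The section also says: "Binary logistic regression and multiple linear regression will be used to assess the effect of intervention". It does not say which outcomes these regressions are for. Neither section mentions a KAP score, a cut point or a rule for many items.

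Under Outcome of the study, KAP is the fourth of four ways in which the main outcome is assessed. The Expected outcome section anticipates that KAP will improve.

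**The concern.** The protocol asks whether KAP as a whole improves, but the tests it names for KAP act on categories. In its standard form McNemar's test needs paired yes/no data. To use it on this questionnaire, an analyst must either test items one at a time or reduce a total to two groups.

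Tested one at a time at 0.05, some of the 40 items are likely to look improved by chance, and a list of significant items does not show whether KAP changed overall. A cut total throws away much of the variation between pupils, and a cut that is not named can be chosen after the data are seen. Of the four measures, KAP lies closest to the sixteen teaching sessions, so weakening it is costly.

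**Working it through.** The protocol gives no power, error rate or expected difference for KAP, so there is no figure of its own to reproduce. Its sample size concerns malnutrition prevalence; only the 180 pupils per arm are taken from it.

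**Inputs**

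- Items: 24 and 16 (Data collection tool/instrument).
- Threshold: 0.05 per test (Data analysis plan).
- Pupils: 180 per arm, 90 per school (Sample Size & Sampling Strategy).
- Correlation between items: not given; assumed 0 to 0.5.
- Cut point, if any: not given; assumed 50th to 90th percentile.

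**1. Item by item, no effect on any item**

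Expected false positives = k × 0.05. For 40 between-arm tests: 40 × 0.05 = 2.0, whatever the correlation.

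Chance of at least one, independent items = 1 − 0.95^k:

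- 40 items: 1 − 0.95^40 = 0.871
- 24 nutrition items: 1 − 0.95^24 = 0.708
- 16 WASH items: 1 − 0.95^16 = 0.560

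Simulation of 40 equally correlated two-sided tests:

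| Correlation | Chance of at least one |
|---|---|
| 0 | 87% |
| 0.1 | 85% |
| 0.2 | 81% |
| 0.3 | 74% |
| 0.5 | 57% |

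A second simulation used 40 yes/no items, each with 50% positive, 180 per arm, and chi-square tests. With latent correlations of 0.1, 0.3 and 0.5 it gave about 87%, 82% and 72%. The two agree: a latent correlation of 0.5 split at the median leaves a correlation of (2/π) × arcsin(0.5) = 0.33 between the yes/no items, and the table gives 74% at 0.3. Within-arm McNemar tests would add to these counts.

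For comparison, two scores tested at 0.05 give 1 − 0.95² = 0.098 if independent.

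**2. A roughly normal total split at a cut**

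Efficiency relative to the full score, at percentile q = φ(z_q)² / [q(1 − q)]:

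- median: 0.3989² / 0.25 = 0.64
- 80th percentile: 0.49
- 90th percentile: 0.34

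In terms of power: with 180 per arm, a score difference of (1.960 + 0.842) × √(2/180) = 0.295 SD has 80% power. Split at the median, this becomes 50.0% against 61.6%, with 60% power. Returning to 80% needs 286 per arm, and 180/286 = 0.63, in line with the 0.64 above.

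**3. School as the randomised unit**

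Steps 1 and 2 treat pupils as independent. Four schools are randomised, so the design effect is 1 + 89 × ICC. The protocol gives no ICC. At an assumed 0.01 the design effect is 1.89, and a pupil-level test at nominal 5% rejects with probability 2 × [1 − Φ(1.96/√1.89)], about 15%. At 0.05 the design effect is 5.45 and the rate about 40%. Baseline adjustment may reduce this. It affects item tests and a plain regression on a score alike.

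**The case against.** The best defence is that the protocol never says 40 items will be tested one by one, nor that a total will be cut. Linear regression is listed with no outcome named, KAP is a listed outcome, and a regression on a KAP score is therefore possible. A scoring key is commonly left to a statistical analysis plan, and the questionnaire may still be amended after pilot testing. KAP also appears in neither the primary nor the secondary objective, and the hypotheses concern malnutrition prevalence.

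Much of this stands. A reader might infer that the plan commits to item-by-item testing or rules out a score; the text supports neither. A reader might also infer that false-positive items are near certain. The 87% needs 40 separate tests, independent items and no effect on any of them, and items from one questionnaire are likely to be correlated.

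What does not stand is that nothing has been fixed. The table places KAP with the categorical tests and apart from continuous variables. That is a stated choice, and a regression assigned to no outcome does not undo it. The prose of the same section offers McNemar for variables that are not normally distributed, but the test does not analyse a skewed score, so this gives no other route.

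**Conclusion.** The point holds in a limited form. The protocol ties KAP only to percentages and to chi-square and McNemar tests at 0.05, and does not say how 40 items become a result.

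- If items are tested separately and nothing changes, 2 false positives are expected among 40 between-arm tests. The chance of at least one is about 57% to 87% for an assumed between-item correlation of 0.5 down to 0. Likely is the right word.
- If a roughly normal total is cut instead, efficiency is at best about 64%, at the median, and lower at more extreme cuts.

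Both figures are conditional, because the protocol states neither route. Both ignore clustering by school, which would raise the false-positive rate further if the tests ignore it. The malnutrition hypothesis is not affected. The point is worth correcting because KAP is listed as a measure of the main outcome and the data for a better analysis are already being collected.

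**What to change.** Before end-line data are seen, and once pilot testing has settled the items:

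- Define a nutrition score from the 24 items and a WASH score from the 16, with a written scoring key. Whether knowledge, attitude and practice belong in one total is debatable, so report their sub-scores as description.
- Compare arms on each score with a linear regression adjusted for the baseline score. A plain pupil-level model is not enough: the regression should follow whatever approach the trial adopts for its four randomised schools.
- Name these regressions in the data analysis plan as the KAP comparison, in place of the chi-square and McNemar entry.
- Show item percentages by arm and time point without p-values.

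This needs a scoring key and one paragraph, and no new data. The downside is that claims of significance for single items are given up.

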**b. Dependent variables/Outcome of study**

1. Body Mass Index: All school going 6- 8 grade adolescents will undergo anthropometric measurements such as height, and weight (BMI). The measurement will be taken at baseline and end line by using WHO standard growth chart.
2. Micronutrients: Blood sample will be collected twice (baseline and end line) from a subset of 108 adolescents (54 intervention group,54 control group). The blood samples will help to assess the impact of intervention on micronutrient deficiencies (Iron, Zinc, Calcium, CBC, Vitamin D)
3. Physical examination: Physical examination like hair, skin, nail, eye (bitot spot), mouth (dental caries), and goiter will be assessed for micronutrient deficiencies at baseline and end line.
4. Knowledge, attitude, and practices regarding nutrition and WASH: a structured questionnaire will be used to collect data on nutrition and WASH-related indicators. The survey will be administered at baseline and end line. The indicator assessed will be adolescent health status and knowledge, attitude, and practices regarding nutrition and WASH practices.

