### **Secondary objective**

To measure the impact of school-based nutrition education and water, sanitation, and hygiene intervention on micronutrient levels among early adolescents.

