### **Study Setting**

For this study, public schools (boys and girls) in Gojra will be selected. There are 40 public schools (20 boys and 20 girls) in Gojra. We will invite the schools for study projects that fulfill the eligibility criteria (inclusion and exclusion criteria). From these willing schools, four public schools that are at least 1-2 Km away from each other (two boys and two girls) will be randomly selected via balloting. The inclusion criterion related to distance is intended to reduce contamination between schools of different arms. These four schools (boys and girls) will then be randomly assigned to either the school (one boy and one girl) with the intervention or to the school (one boy and one girl) without the intervention (Control school).

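### The analysis plan compares unmatched arms with a paired t-test and gives McNemar's test to non-normal variables; neither test fits the use stated

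*Protocol*

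**What the plan says.** Four statements in the protocol's Data analysis plan (Phase II, RCT phase) bear on this.

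- On comparing the arms: "The comparison between intervention and control at baseline and end line will be performed by using paired t-test and Chi-square".
- On non-normal data: "For the variables that are not normally distributed, a nonparametric test McNamara will be used". The name is read here as McNemar.
- On the treatment effect: "Binary logistic regression and multiple linear regression will be used to assess the effect of intervention". No outcomes are attached to either model.
- On description: "median with interquartile range will be mentioned for qualitative variables".

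The table below that text lists the paired t-test for continuous variables and no other t-test. It puts "Chi-Square-McNamara" against knowledge, attitude and practices (KAP), and the median with interquartile range against skewed distributions.

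On the design, Study Setting says "These four schools (boys and girls) will then be randomly assigned to either the school (one boy and one girl) with the intervention"; the other two schools are controls. The outcome section says "Blood sample will be collected twice (baseline and end line) from a subset of 108 adolescents", 54 per group, and has BMI measured at the same two times. The secondary objective is "To measure the impact of school-based nutrition education and water, sanitation, and hygiene intervention on micronutrient levels among early adolescents".

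**The concern.** A paired t-test needs a one-to-one link between the values compared. Nothing in the protocol links a pupil in an intervention school to a pupil in a control school, so the test named for comparing the arms cannot be run as described. The pairs that do exist are each pupil's own baseline and end-line values, and a test on those answers a different question: whether one arm changed.

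That reading is a real risk here. The table of baseline-assessment activities describes the purpose of the blood tests as finding deficiency at baseline and improvement at end line, which invites a before/after claim. These pupils are also growing between measurements, so BMI may move in both arms whatever the intervention does.

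McNemar's test compares paired binary responses. It cannot be applied to a skewed zinc or vitamin D level, so the sentence on non-normal variables gives such values no usable test. At stake are the between-arm results for continuous BMI and for the micronutrient levels of the secondary objective.

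**Working it through.** **1. The passages side by side**

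| Item | Text of the analysis plan | Table of the analysis plan | What the design supplies |
|---|---|---|---|
| Paired t-test | Intervention against control | Continuous variables | Pairs only within a pupil, baseline and end line |
| McNemar | Variables that are not normal | KAP | Paired binary items within a pupil |
| Median, IQR | Qualitative variables | Skewed distributions | Skewed continuous variables |
| Regression | Effect of intervention | Listed, no outcome given | A valid form of between-arm comparison, apart from school clustering |

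The text and table disagree on McNemar and on the median. The comparison sentence disagrees with the regression sentence about which method compares the arms. The plan gives no figure on this point to reproduce.

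**2. What the before/after reading would do**

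Inputs from the protocol: n = 54 per arm (micronutrients), n = 180 per arm (BMI), two-sided 5%. Assumptions: no intervention effect, a shift common to both arms, independent pupils. The protocol gives no shift, so a range is shown.

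Let d = common shift / SD of change. The paired t statistic is noncentral t with n − 1 degrees of freedom and noncentrality d√n. Let p be the chance that one arm is significant. With independent arms, the chance that the intervention arm is significant and control is not is p(1 − p).

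For d = 0.2:
- n = 54: noncentrality 0.2 × √54 = 1.47, p = 0.303, p(1 − p) = 0.303 × 0.697 = 0.211.
- n = 180: noncentrality 0.2 × √180 = 2.68, p = 0.761, p(1 − p) = 0.761 × 0.239 = 0.182.

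| d | n = 54: p | n = 54: p(1 − p) | n = 180: p | n = 180: p(1 − p) |
|---|---|---|---|---|
| 0.1 | 0.111 | 0.099 | 0.266 | 0.195 |
| 0.2 | 0.303 | 0.211 | 0.761 | 0.182 |
| 0.3 | 0.581 | 0.243 | 0.979 | 0.020 |
| 0.5 | 0.950 | 0.047 | >0.999 | about 0.000001 |

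At n = 180 the one-arm-only pattern vanishes for large shifts because both arms are then nearly always significant. The within-arm test on its own is then significant almost every time with no intervention effect.

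**3. What a between-arm regression would do in the same setting**

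End-line value regressed on arm, baseline and sex; d = 0.2; no arm effect; independent pupils; 20,000 simulated trials per setting; baseline to end-line correlations 0.3 / 0.6 / 0.9:
- 54 per arm: rejects 0.051 / 0.052 / 0.050.
- 180 per arm: rejects 0.048 / 0.047 / 0.050.

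In the same runs the one-arm-only pattern occurred in 0.215 / 0.213 / 0.212 and 0.186 / 0.183 / 0.182, which agrees with step 2.

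**4. Limit of step 3**

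The 5% depends on independent pupils. With m pupils per school and intraclass correlation ICC, the design effect is D = 1 + (m − 1) × ICC, and a nominal 5% test that ignores schools has error of about 2[1 − Φ(1.96/√D)]. The ICC is an assumption.

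| ICC | m = 90: D | m = 90: error | m = 27: D | m = 27: error |
|---|---|---|---|---|
| 0.01 | 1.89 | 15% | 1.26 | 8% |
| 0.02 | 2.78 | 24% | 1.52 | 11% |
| 0.05 | 5.45 | 40% | 2.30 | 20% |

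Here 90 is the protocol's number per school, and 27 = 54/2 assumes that the blood subset is split evenly between an arm's two schools.

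**The case against.** The strongest reply is that the effect analysis is already stated. The plan ties logistic and linear regression to the effect of the intervention, and the prevalence hypothesis keeps chi-square and logistic regression. On this view one paragraph is badly worded and no primary test fails. That stands, and it limits the severity. It does not cure the two sentences: the regression sentence names no outcomes and does not confine the paired tests to within-arm use, so an analyst who follows the explicit comparison sentence runs the wrong test.

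Second, both tests have legitimate uses here, and the table's entries are compatible with them: the paired t-test for change within an arm, McNemar's test for binary KAP items. Micronutrient deficiency, taken as a binary status, could also be handled by tests the plan names. This is fair, but the text assigns the tests otherwise, and the secondary objective concerns levels.

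Third, the protocol nowhere says that significance in one arm only will be read as an effect, so the 18% to 21% prices a possible misreading at an assumed shift. That also stands: the figures illustrate the risk and do not measure a stated decision rule.

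Fourth, the recommended regression holds 5% only if pupils are independent, and four schools are allocated, two per arm. This is correct, and step 4 of the working shows the size. It is a separate defect, and it does not make the paired t-test a comparison of arms.

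Finally, covariate choice and transformation are often left to a statistical analysis plan, and rank-based methods could serve for skewed values. The specific model below is therefore one workable choice; the error to correct is the assignment of tests.

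**Conclusion.** The concern holds. As written, the comparison sentence names a test that either has no pairs or does not compare arms, and the McNemar sentence gives skewed continuous variables a test that cannot be applied to them and conflicts with the table. The fault is confined to those sentences and affects continuous BMI and micronutrient levels, not the prevalence hypothesis.

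Under the before/after reading, with no intervention effect, independent pupils and assumed common shifts, a result significant in the intervention arm only arises by chance 5% to 24% of the time at 54 per arm (0.1 to 0.5 SD of change) and 2% to 20% at 180 per arm (0.1 to 0.3 SD, and essentially never at 0.5). This should be fixed. It is not fatal, because a suitable form of between-arm analysis is already named.

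**What to change.** Reword the paragraph as follows.

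- **Between-arm analysis, continuous outcomes:** linear regression of end-line BMI and of each micronutrient level on arm, adjusted for the baseline value and sex, with skewed values log-transformed.
- **Between-arm analysis, malnutrition status:** logistic regression, as the analysis for the prevalence hypothesis. The protocol's anthropometric categories include thin and obese pupils, so opposite movements can cancel in mean BMI, and mean BMI cannot replace prevalence.
- **Within-arm description only:** paired t-test for continuous variables and McNemar's test for binary KAP items.
- **Consistency with the table:** assign McNemar to KAP items and the median with interquartile range to skewed variables.

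The cost is one reworded paragraph. It needs no new data, since baseline values are already planned and sex is known from the single-gender schools. The rewording does not deal with allocation by school, two per arm. That needs its own treatment, and the regression should not be presented as holding 5% error until it has it.

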According to the 2018 National Nutritional Survey (NNS) in Pakistan, adolescent (10-19 years) boys are more affected than girls in terms of being underweight, and more adolescent girls are overweight compared to their male peers. The prevalence of malnutrition across Pakistan varies from one region to the other. All provinces have different rates of malnutrition, the underweight population in Sindh province is higher as compared to other provinces, while the prevalence of obesity on the other hand is high in Baluchistan and KP provinces of Pakistan along with NMD (newly merged districts). In Punjab province, more adolescent boys are underweight than girls.

Survey also showed that 56.6 % of adolescent girls in Pakistan are anemic (NIPS & ICF 2019).

All over Pakistan, the high prevalence of both underweight and overweight/ obese adolescent populations is a major concern and requires serious attention to addressing all forms of malnutrition-associated disorders. According to a report, micronutrient deficiencies and malnutrition were observed in young women between the ages of 15-19 years and children under five years of age. However, the early adolescent female group and males aged between 10- 19 years were not studied in this group for micronutrient assessment, although this age group is 23 % of Pakistan's total population. The early adolescent group (age 10-14 years) consists of almost 12 % of the total population of Pakistan (NIPS & ICF 2019).

The physical and mental growth and learning abilities of adolescents are influenced by many factors. These factors include the health condition of the adolescents and their perception of their health practices, school environment, socio-economic status of their parents, and nearby facilities of health services. The most important factor influencing the health, mental growth, and

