### **Sample Size & Sampling Strategy**

The sample size was calculated by using PASS software. Sample sizes were estimated to change in nutritional status of early adolescent boys and girls. A sample size of 360 adolescents

(180 in each intervention and control group) will achieve 80% power assuming 42% malnutrition among students in the control arm and at least 6% reduction in the intervention arm having 90 students from each school at a two-sided 5% level of significance.

To assess the micronutrient levels (Iron, Zinc, Calcium, CBC, and Vitamin D) through a blood sample, a subset of 108 adolescents 6-8 grade school going adolescents (54 intervention group, 54 control group) from this total sample size (360) will be selected through random selection.

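### The analysis plan gives the arm comparison a within-pupil paired test and does not say that the effect regressions adjust for the pupil's baseline value

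*Protocol*

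**What the plan says.** Three analysis statements stand in the Data analysis plan of Phase II.

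- The arm comparison: "The comparison between intervention and control at baseline and end line will be performed by using paired t-test and Chi-square".
- The non-normal case: "For the variables that are not normally distributed, a nonparametric test McNamara will be used" (evidently McNemar's test). The table in that section repeats the paired t-test for continuous variables and the chi-square/McNemar pair for knowledge, attitude and practice (KAP) items.
- The effect model: "Binary logistic regression and multiple linear regression will be used to assess the effect of intervention". No outcome, covariate, baseline term or school term is named for it.

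Baseline values will exist. For height, weight and BMI, the outcome section says "The measurement will be taken at baseline and end line by using WHO standard growth chart". Physical signs and the KAP survey are also taken twice, as are micronutrients in a subset.

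On allocation, Study Setting says "These four schools (boys and girls) will then be randomly assigned to either the school (one boy and one girl) with the intervention"; the other boys' school and girls' school are the controls. The sample size section plans 180 pupils per arm, takes control prevalence as 42%, and looks for "at least 6% reduction in the intervention arm having 90 students from each school at a two-sided 5% level of significance".

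**The concern.** Taken one by one, none of the stated analyses is a baseline-adjusted comparison of the arms.

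- The paired t-test and McNemar's test use the pupil's own baseline, but they test change within a group. Assigning the paired t-test to an intervention-control comparison is an error in the text.
- A chi-square test of the arms at each time point compares the arms but ignores the pupil's earlier value.
- The regressions could supply the missing analysis, but the text does not say that they do.

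This matters because only two schools form each arm, so balance at baseline cannot be relied on. If one arm starts with more malnutrition, an end-line comparison inherits much of that difference, and it can be read as harm or benefit. A significance test of the arms at baseline does not correct it. Precision available from planned measurements would also be given up.

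**Working it through.** **The plan's own figure.** The protocol gives no baseline gap, ICC or baseline/end-line correlation, so there is no figure to reproduce on this point. Its nearest figure is 80% power with 180 per arm. For 42% against 36%, two-sided 5%, pooled variance:

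z = (0.06 × √180 − 1.96 × √(2 × 0.39 × 0.61)) / √(0.42 × 0.58 + 0.36 × 0.64) = (0.805 − 1.352) / 0.688 = −0.79, so power is about 21%.

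The 80% is not reproduced. That is a separate matter which neither supports nor weakens this point, and nothing below uses it.

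**Inputs.** From the protocol: prevalence p = 0.42, m = 90 pupils per school, k = 2 schools per arm, target reduction 6 points (read as absolute). Assumed: ICC 0 to 0.10; r, the correlation of a pupil's baseline and end-line values, 0.5 to 0.9.

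**Step 1: chance baseline gap between arms.**

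SD = √[2p(1 − p)(1 + (m − 1) × ICC) / (km)]

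At ICC 0 this is √(2 × 0.2436 / 180) = 0.052. The chance that the gap exceeds 6 points in either direction is 2 × (1 − Φ(6/SD)), with SD in points.

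| ICC (assumed) | 1 + 89 × ICC | SD of gap (points) | Chance of gap above 6 points |
|---|---|---|---|
| 0 | 1.00 | 5.2 | 25% |
| 0.01 | 1.89 | 7.2 | 40% |
| 0.02 | 2.78 | 8.7 | 49% |
| 0.05 | 5.45 | 12.1 | 62% |
| 0.10 | 9.90 | 16.4 | 71% |

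**Step 2: how much of a gap reaches the result.** With equal spread at both times, an end-line-only comparison carries on average r × gap. For a 6-point gap this is 3.0, 4.2 or 5.4 points at r = 0.5, 0.7 or 0.9. Adjusting for the baseline value removes that expected part, provided r also describes how school differences persist.

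**Step 3: precision in the linear models.** Adjustment multiplies the pupil-level residual variance by 1 − r²: 0.75, 0.51 or 0.19 at r = 0.5, 0.7 or 0.9. The pupil-level standard error falls by 1 − √(1 − r²): 13%, 29% or 56%.

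This is not the gain in the total standard error when schools differ. At ICC 0.05 the variance parts are proportional to 0.95/180 = 0.0053 (pupils) and 0.05/2 = 0.025 (schools), so pupils contribute about 17%. If the school part did not change, the total standard error would fall by 1 − √(0.83 + 0.17 × 0.51), about 4%, at r = 0.7 and by about 7% at r = 0.9. Any reduction of the school part by adjustment is not quantified here.

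**The case against.** The strongest reply is that covariate lists commonly belong in a statistical analysis plan, which is not at hand, and that multiple regression implies more than one predictor. This stands in part. A reader might infer that the regressions leave out the baseline value and sex. The protocol does not say so; it lists no covariates at all. What remains is text that the protocol does fix: a within-pupil test given to the between-arm comparison. A later plan that compared arms with baseline adjustment would have to depart from it.

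Four further limits stand.

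- **The baseline is used.** A reader might infer that the plan ignores it except to compare arms at the start. The paired t-test and McNemar's test do use it. The sentence can even be read as a before-after comparison within each arm, but that reading gives no arm contrast either.
- **Sex does not create the gap.** Each arm has one boys' and one girls' school of equal planned size, so sex is balanced. The Introduction reports that "adolescent (10-19 years) boys are more affected than girls in terms of being underweight", but also that more girls are overweight. Both count as malnutrition here, so the passage does not show that sex predicts malnutrition overall.
- **The gap is not bias in itself.** At ICC 0 the 25% is ordinary sampling variation, which a valid end-line test already covers in its standard error. At higher ICC the validity problem is clustering left unhandled, which is a separate matter.
- **The variance gain is limited.** The 1 − r² factor belongs to the pupil-level part of linear models and should not be quoted for the logistic model of malnutrition status.

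**Conclusion.** The point holds in this form: the plan assigns a paired test to the intervention-control comparison and does not state that the effect regressions adjust for baseline, so no analysis as written gives a baseline-adjusted effect. A chance baseline gap above the 6-point target has a probability of 25% at ICC 0, 49% at 0.02 and 62% at 0.05. These figures rest on an assumed ICC, 42% prevalence, 90 pupils in each of two schools per arm, and an absolute reading of the 6%. The share carried into an end-line-only comparison, r times the gap, rests on an assumed r.

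The documents do not support saying that baseline or sex is excluded from the regressions, or that the result must be biased. Adjustment is a low-cost improvement that should be made. It does not handle clustering, and it does not remove school differences that arise after baseline.

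**What to change.** Replace the sentences on the arm comparison and the regressions with wording such as:

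> The intervention effect is estimated by regressing the end-line value on arm, the pupil's own baseline value of the same measure, and sex. Linear models are used for BMI-for-age, micronutrient levels and KAP scores. A logistic model is used for malnutrition status, adjusted for baseline malnutrition status or for a non-linear term in baseline BMI-for-age. Paired t-tests and McNemar's tests describe change within each arm and are not used to compare arms.

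Sex enters because schools are allocated within it, for precision and consistency with the design. A single linear term in baseline BMI-for-age would not suit malnutrition status, because thinness and overweight both count and risk is raised at both ends. The report should say that the adjusted logistic model gives a conditional odds ratio, which differs from the unadjusted one even without imbalance.

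The cost is a few sentences. The measurements are already planned, the paired tests already require each pupil's two records to be linked, and SPSS fits these models. Handling of school clustering must be settled separately.
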